All participants in this study are adults and informed consent will be obtained. No vulnerable populations are selected for this study other than women of child bearing potential. The concerns for pregnant women to receive oxytocin will be discussed as part of the consent form signing. A pregnancy test will be obtained prior to the beginning of the treatment.

Anytime consent is obtained, it is incumbent on the individual obtaining the consent to ascertain whether the potential participant understand all aspects of the study. Obtaining informed consent is an interactive process with questions asked of both the investigator and potential participant. A participating investigator or his designee will obtain informed consent and sign the consent form.

All tests will be coded. The database linking coded samples to subject identity will be password-protected, access to which will be limited to essential study staff. Personal identifying information will be recorded in a secure database and consents or other pertinent clinical information stored in a secure file at TCH. Identifiable subject-specific data will not be reported in any public format, nor will it be reported to any third party to which Baylor may contract

E3. Pregnant woman/fetus

Will pregnant women and/or fetuses (as described in 45 CFR 46 Subpart B) be enrolled in the research? No

E4. Neonates

Will neonates of uncertain viability or nonviable neonates (as described in 45 CFR 46 Subpart B) be enrolled in the research? No

E5. Children

Will children be enrolled in the research?

No

Section F: Design/Procedure

F1. Design

Select one category that most adequately describes your research:

c) Pilot

Discuss the research design including but not limited to such issues as: probability of group assignment, potential for subject to be randomized to placebo group, use of control subjects, etc.

This will be a single-site, single-blind, fixed-sequence study to evaluate the effect of IV oxytocin on chronic pain in female adult patients with hypermobile EDS.

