1) Premenopausal Females, Age >18 years 2) Clinical diagnosis of hypermobile EDS according to the 2017 criteria for hEDS 3) Menstrual periods (range from 8 to 42 days) 4) Pain level greater that pain score of 4 out of 10 on a Numeric Rating Scale in at least two of the following locations: back, neck, shoulders, elbows, wrist, hand joints, hips, knees, ankles, on most days over the 3 months preceding enrollment. 5) On a stable regimen for pain control without any expected increase in dose of pain medications during the study period. 6) All participants should have a negative urine pregnancy test and agree to use an acceptable method of contraception (abstinence or barrier methods). 7) Current from the last year EKG report prior to the infusion for screening purposes. Otherwise, participant will need to have an EKG done in person at the screening visit on site.

Exclusion Criteria:

1) Known allergy to OXT or preservatives in the medication 2) Pregnancy 3) Lactation 4) A confirmed clinical diagnosis of autoimmune disorders that lead to joint inflammation and joint pain such as SLE, RA, psoriatic arthritis, ankylosing spondylitis, scleroderma, and enteropathic arthritis 5) History of known cardiac arrhythmias (except for asymptomatic sinus tachycardia and sinus bradycardia) 6) Heart rate persistently greater than 110/min or less than 50 per minute 7) QTC of > 450 ms from EKG (electrocardiogram) test 8) Taking oral or other hormonal contraceptives 9) Individuals with a clinical condition which, in the view of the investigator compromises safety 10) Participating in another interventional study.

F2. Procedure

This will be a single-blind, fixed-sequence study. This study will include two treatment periods. During the first period, placebo will be administered and during the second period, oxytocin will be administered. The participants will be blinded to the sequence of treatment assignment.

Each treatment period will start 7-12 days after the first day of menstruation and will be divided to the following: 1) preinfusion period of 6 days during which baseline pain and anxiety evaluation will be done, 2) infusion period that includes 3 consecutive days of infusions, 3) post-infusion evaluation period of 6 days during which post-treatment pain and anxiety will be evaluated.

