Pain and anxiety evaluation will be done using the following questionnaires: 1) The Brief Pain Inventory (BPI), 2) Numerical Rating Scale (NRS), 3) McGill Pain Questionnaire, 4) Hospital Anxiety and Depression Scale (HAD), and 5) State-Trait Anxiety Inventory (STAI- trait part) (see section S). Questionnaires will be sent to subjects by secure e-mail, physical mail, or will be handed to the subjects at the beginning of the research period. Subjects will be instructed to complete these questionnaires and return to study staff.

Schedule of Assessments (refer to attachment in section S). This will be provided to study staff only.

Pre-Screen: Eligibility screening of subjects will be done prior to study enrollment. Interested participants will be consented by phone to screen for eligibility purposes.

Eligibility screening will involve: 1) medical record review, 2) collecting history of pain relevant to inclusion, 3) informing patients that pain medication regimens should continue without change during the two weeks prior to the study and throughout the study duration.

Screen Visit: If participants are deemed appropriate candidates for the study, they will come to the study site at BCM/St. Luke's for a screening visit. The screen visit to take place at least one day before the infusion. During the screening visit, the following procedures will be done: 1) signed informed consent, 2) history and physical examination, including vital signs, 3) review of concomitant medications, 4) review of medical records, if available, 5) Urine pregnancy test will be administered, and 6) EKG for assessment of QTc. QTc will be calculated by Fredericia formula. (Current EKG report from the last year prior to the infusion will be used for screening purposes in place of in-person EKG at screen visit.) 7) Enrollment checklist will be completed and 8) receive Actiheart device after study staff goes over instructions for device use. (Actiheart device for monitoring heart rate and movement will be affixed to the chest of the participant with two electrodes. This will be worn for 9 days during the course of the study. if for some reason participants cannot maintain wearing the monitor for 9 days, the study will still proceed.)

Treatment period 1 will start soon after the end of menstrual period for subjects. Treatment period 1 will consist of the following:

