- A. Pre-infusion Period 2 (will last six days prior to infusion): 1) Questionnaires: Subjects will be asked to complete painevaluation questionnaires (BPI, NRS, and McGill). Anxiety evaluation will be completed by patients using HAD and STAltrait and state parts questionnaires. 2) Participants will be asked to wear the ACTIHEART device during 3 days prior to the infusion, during the 3 infusion days, and in the three days after the infusion.
- B. Infusion period 2 (oxytocin Infusion over three days): Participants will arrive for three consecutive day visits. 1) Subject will be instructed to eat a light, non-fatty breakfast. 2) Vital signs (blood pressure and heart rate), including weight and height will be collected prior to infusion. 3) Provide two questionnaires (BPI, NRS) for subjects to complete. 4) Nursing staff will establish IV access for infusion and blood collection. 5) Prior to infusion, blood samples will be obtained for oxytocin levels and for storage. 6) Oxytocin infusion (200ml, 0.9% NaCl with 1 IU of oxytocin, over 40 minutes*). Blood pressure and heart rate will be monitored during and after the infusion. 7) Blood sample (for oxytocin levels and storage) will be collected immediately after the infusion on day 1. Note: This will require a second vein access to be set prior to the infusion (this sample cannot be collected from the place of the OXT / Placebo infusion). 8) Administer both the NPI and STAI-state part questionnaires prior to subject's discharge. Subjects will be discharged 2 hours after the infusion.

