According to accepted guidelines, the maximum amount of blood to be drawn over a 24-hour period is 3% of total blood volume if the subject is an outpatient, and 5% of total blood volume if the subject is an inpatient. The maximum amount of blood which can be safely drawn from research participants in any one-month period should not exceed 10% of the total blood volume.

All the participants in this study are adults. On average an adult have blood volume of approximately 5 litres. This will allow us to draw maximum of 150 ml per 24 hours and 500 ml over a total period of one month. The amount of blood planned to be drawn will be lower than the maximum allowed. A record of total blood volume withdrawn during each visit will be maintained in the subject's medical record.

Blood drawn during each treatment period (in one month) include: Day 1: Oxytocin levels (10ml) and storage blood (10ml) at preinfusion, immediately post infusion, and 2 hours post infusion. This sums up to 60 ml per 24 hours. Day 3: Storage blood (10ml) at preinfusion and 2 hours post infusion. This sums up to 20 ml per 24 hours. Total of 80ml per one month.

The risk of blood draw may include bruising, pain and infection at the place where the needle was inserted.

For the EKG test, you may develop a mild rash or skin irritation where the electrodes were attached. If any paste or gel was used to attach the electrodes, you may have an allergic reaction to it. This irritation usually goes away once the patches are removed, without needing treatment.

For the ACTIHEART device - mild skin irritation where the electrodes are attached. We recommend that participants will alternate the place of electrodes every day between two suggested sites.

A risk of loss of confidentiality may be possible but every effort by research staff will be made to reduce or eliminate any risk for the subjects.

H2. Data and safety monitoring plan

Do the study activities impart greater than minimal risk to subjects? Yes

NOTE: The answer to the questions in H2 requires the completion of the form: 'Section H â€" Data and Safety Monitoring Plan' as an attachment in Section S.

H3. Coordination of information among sites for multi-site research

Is the BCM Principal Investigator acting as the SPONSOR-INVESTIGATOR for this multi-site research? No or Not Applicable

Is BCM the COORDINATING CENTER for this multi-site research?

No or Not Applicable

Section I: Potential Benefits

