What is the purpose of the sample collection?

Urine sample will be collected for a urine pregnancy test to determine study eligibility.

For blood draws, specify the amount drawn, in teaspoons, at each visit and across the course of the subjects entire participation time.

N/A

Is there the possibility that cell lines will be developed with this sample? No

Sample will be obtained from:

Other: Research subject

Will the sample be stripped of identifiers?

No

If sample will be released outside the hospital:

Will sample be released to anyone not listed as an investigator on the protocol? Will the information be identifiable, coded or de-identified?

No.

Will sample material be sold or transferred to any third parties? Will the information be de-identified?

No.

If sample will be banked for future use:

Where will the sample be banked and for how long?

Nο

Does the banking institution have an approved policy for the distribution of samples?

No.

If the entire sample will NOT be used during the course of this research study:

Will the remaining tissue be discarded? If not what will be done with the remaining sample after study completion and how long will the sample be kept?

Yes, any remaining urine sample will be discarded once the urine pregnancy test has been administered.

Will samples be made available to the research subject (or his/her medical doctor) for other testing?

No

If a subject withdraws from the study:

Will subject have the option to get the remaining portion of their sample back?

No

Will samples be destroyed? If not, will they be kept anonymously? What will happen to the sample if the subject revokes authorization?

Yes, any remaining urine sample will be discarded once the urine pregnancy test has been administered.

Will data obtained from their sample be deleted? What will happen to the sample if the subject revokes authorization?

If data was collected prior to withdrawal, then that data will be kept. Any data collected after withdrawal will be deleted.

Will study data or test results be recorded in the subject's medical records?

Yes

Will results of specific tests and/or results of the overall study be revealed to the research subject and or his/her doctor?

Results from urine pregnancy test will be reported in hospital electronic medical record system, i.e., BCM EPIC or BSLMC EPIC.

Please identify all third parties, including the subject's physician, to receive the test results.

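### Low severity, cheap to close: the only listed pregnancy test is at screening, so it is at least 29 days old when oxytocin is first infused, and no repeat is listed

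*Combined protocol and SAP*

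**What the plan says.** All references are to the combined protocol and SAP.

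- **The test.** Section F2, Screen Visit, lists it among the screening procedures: "Urine pregnancy test will be administered". On timing: "The screen visit to take place at least one day before the infusion". Section N (Urine) gives its purpose: "Urine sample will be collected for a urine pregnancy test to determine study eligibility".
- **The stated concern.** Section E2: "The concerns for pregnant women to receive oxytocin will be discussed as part of the consent form signing", followed by "A pregnancy test will be obtained prior to the beginning of the treatment". Pregnancy is an exclusion criterion in Section F1.
- **The order.** Sections F1 and F2 fix the sequence for everyone: saline first, oxytocin second.
- **The oxytocin steps.** Section F2, step B of treatment period 2, headed "Infusion period 2 (oxytocin Infusion over three days", lists the breakfast instruction, vital signs, questionnaires, IV access and blood samples ahead of the drug. It lists no pregnancy test.
- **The other safeguards.** The inclusion criteria require abstinence or a barrier method, and hormonal contraceptives are excluded. Section F2 lets period 2 begin only 7-12 days after the onset of a menstruation, and no sooner than two weeks after period 1 is complete.
- **The menstrual criterion.** "Menstrual periods (range from 8 to 42 days" (closing bracket omitted). It does not ask for regular cycles.
- **What is not in the published document.** The Schedule of Assessments and the data and safety monitoring form are attachments in Section S. Of the latter, Section H2 says: "The answer to the questions in H2 requires the completion of the form".

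**The concern.** The sequence is fixed, so the single listed test stands directly before the harmless infusion and a whole period before the active one. The protocol itself excludes pregnancy and names oxytocin in pregnancy as a concern, yet the listed steps do not recheck that condition before the drug is given.

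A screening test on the last permitted day falls in the middle of the period 1 cycle and cannot show a conception in that cycle. From then until oxytocin, the written plan relies on contraception and on a bleed being correctly recognised as menstruation. At stake is the safety of a participant and a possible pregnancy. The efficacy analysis is not affected. The documents give no estimate of fetal harm at 1 IU over 40 minutes, and none is assumed here.

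**Working it through.** The plan states no figure for the age of the test, so there is none to reproduce. What follows is day counting from its own intervals.

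**Inputs (Section F2).** A treatment period is 6 pre-infusion days, 3 infusion days and 6 post-infusion days. Period 2 begins at least 14 days after period 1 is complete, and each period begins 7-12 days after menstruation onset. Screening is at least 1 day before the first infusion.

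**Minimum age of the test.** Let day 1 be the first pre-infusion day of period 1.

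- Saline: days 7-9. Post-infusion evaluation: days 10-15.
- Latest permitted screening: day 7 - 1 = day 6.
- Earliest start of period 2: day 15 + 14 = day 29.
- First oxytocin, after six pre-infusion days: day 29 + 6 = day 35.
- Age of the test: 35 - 6 = **29 days**.

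An earlier screening visit adds day for day.

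**With the menstruation rule, 28-day cycle.** Let s1 and s2 be the days from menstruation onset to the start of each period, each between 7 and 12. With one new menstruation, start-to-start = 28 + (s2 - s1). This can run from 23 to 33 days, but the two-week gap requires at least 29 - 1 = 28, which leaves 28-33. Age of the test = (start-to-start + 6) - 5 = start-to-start + 1, so **29-34 days**.

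**With the other spacing statement.** Section N (Blood) says that the periods are at least one month apart. Taking a month as 28-31 days (my assumption):

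- Start to start: age 28 + 1 to 31 + 1 = 29-32 days at least.
- End to start: first oxytocin on day 15 + 28 + 6 = 49 to day 15 + 31 + 6 = 52, so age 43-46 days at least. One 28-day cycle reaches only 33 days start to start, short of the 42-45 needed. Two cycles give 56 ± 5 = 51-61 days, and an age of 52-62 days.

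**What the screening test can see.** The latest screening falls 7 + 5 = 12 to 12 + 5 = 17 days after onset of the period 1 menstruation. That is too early to show a conception in that cycle.

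**What a repeat test can see.** The first oxytocin infusion falls 7 + 6 = 13 to 12 + 6 = 18 days after onset of the menstruation used to schedule period 2. A test that day comes at least 13-18 days after any conception that preceded the bleed, so it addresses bleeding mistaken for menstruation. It would not show a conception in the current cycle.

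**Effect of the fix.** The age of the latest test at first oxytocin falls from at least 29 days to 0.

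**The case against.** The strongest objection is that the plan already handles this. Before oxytocin, a participant must have tested negative, agreed to abstinence or a barrier method, and had a new menstruation, which staff must date in order to schedule period 2. That menstruation largely resets the question, so the age of the earlier test overstates the risk. What is left is a contraceptive failure in the earlier cycle together with a misread bleed, among 20 women. Most of this stands, and it is why the severity is low. However, the menstruation appears only as a timing rule: no listed step treats it as a pregnancy check or says what to do if the bleeding is atypical. The wide menstrual range accepted, without a requirement for regularity, makes a misread bleed more plausible.

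A second objection is that visit procedures may be set out in Section S. This also stands. A reader might infer that participants are never retested, but the documents do not support that: the attachments are not in the published text, and a repeat test in them cannot be ruled out.

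A reader might also infer that the plan breaks its own promise in Section E2. It does not, because a test at screening precedes both saline and oxytocin.

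Third, the 29 days depend on what counts as a period. Section F1 speaks of the six evaluation days as preceding a period. If a period were the three infusions alone, the gap would run from last saline to first oxytocin, and the age would be 1 + 2 + 14 = 17 days. Section F2 expressly counts both evaluation phases within the period, so 29 is the better minimum. The absence of a listed repeat is the same on either reading.

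Finally, a test added only in period 2 could hint to participants that this is the active period, in a trial with a subjective primary outcome. That is correct, and the fix must allow for it.

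**Conclusion.** The point holds as a cheap, low-severity safety improvement. In the published text the only listed pregnancy test is the eligibility test at screening. It is at least 29 days old at the first oxytocin infusion, 29-34 days for a 28-day cycle, and longer if the one-month spacing in Section N runs from the end of one period to the start of the next. No listed step rechecks pregnancy before the drug.

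This rests on three conditions: Section F2's definition of a period, screening on the last permitted day, and no repeat test in the Section S attachments. Test age describes the gap but does not measure the risk. It should not be read as 29 unguarded days, because a new menstruation and the contraception requirement lie in between. The residual risk is mainly an earlier-cycle pregnancy with bleeding taken for menstruation. Its probability cannot be estimated from the documents.

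**What to change.** First check the Schedule of Assessments in Section S. If it already has a test before each infusion period, only the text needs aligning.

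Otherwise, in Section F2, add to step B of both treatment periods, before IV access on the first infusion day: urine pregnancy test; do not infuse if positive. Make it the same in both periods, so that the test does not mark out the oxytocin period to blinded participants. Align Section E2 (test at screening and before the first infusion of each period) and Section N, Urine (to determine eligibility and to confirm it before each infusion period).

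The cost is about 20 × 2 = 40 urine tests, using an existing study procedure at visits already attended. Sample size and analysis do not change. The limitation is that a conception in the current cycle would still go undetected, so the contraception requirement must stay.

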In this study, we seek to investigate the potential effect of IV oxytocin on chronic pain and its functional consequences in individuals with hypermobile Ehlers Danlos syndrome. Chronic pain will be assessed both by pain scales and by patient-reported outcomes. Functional consequence of chronic musculoskeletal pain will be evaluated using ACTIHEART - a chest-worn device using self-adhesive ECG electrodes that records heart rate, inter-beat-interval (IBI), and physical activity.

Section D: Purpose and Objectives

The purpose of this pilot study is to evaluate effect of IV oxytocin on chronic pain in patients with hypermobile Ehlers Danlos syndrome. The study will evaluate chronic pain before and after treatment with IV oxytocin.

Primary outcome measure 1) Change in the individual's subjective reported pain following treatment with placebo

compared to the change in reported pain following treatment with oxytocin as assessed by the following questionnaires: Numerical pain rating scale, Brief Pain Inventory, and McGill Pain Questionnaire.

Secondary Outcome measures 1) Change in heart rate patterns and activity level following treatment with placebo compared to the change in heart rate patterns and activity level following treatment with oxytocin as an objective functional outcome of pain. 2) Change in reported signs of depression and anxiety following treatment with placebo compared to the change in the reported signs following treatment with oxytocin as assessed by Hospital anxiety and depression scale and State-Trait Anxiety Inventory questionnaires.

Section E: Protocol Risks/Subjects

E1. Risk Category

Category 2: Research involving greater than minimal risk, but presenting the prospect of direct benefit to the individual subjects.

E2. Subjects

Gender:

Female

Age:

Adult (18-64 yrs)

Ethnicity:

All Ethnicities

Primary Language:

English

Groups to be recruited will include:

Patients

Which if any of the following vulnerable populations will be recruited as subjects?

Vulnerable populations require special protections. How will you obtain informed consent, protect subject confidentiality, and prevent undue coercion?

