- C. Post Infusion Period 2 Pain & Anxiety Evaluation for 6 days: Participants will complete questionnaires over six days at the investigator's discretion: BPI, NRS, McGill on days 1, 3, and 5 after infusion and HAD and STAI-state and trait questionnaires on day 6 after infusion. Participants will be instructed to mail back the device after completing three days of their last infusion using a prepaid FedEx air bill that will be sent to them by study staff. *Note: The dose oxytocin administration is based on the American College of Obstetricians and Gynecologists' (ACOG) Practice Bulletins for postpartum hemorrhage (see addendum). From the bulletin: Many organizations have recommended active management of the third stage of labor as a method to reduce the incidence of postpartum hemorrhage. Prophylactic oxytocin, by dilute intravenous infusion (bolus dose of 10 units), or intramuscular injection (10 units), remains the most effective medication with the fewest adverse effects". This clinical protocol allows the administration of bolus of oxytocin in a rate of 333 mU/min. We will administer only 1 unit of oxytocin over 40 minutes rate of 25mU/min to avoid any adverse effects.

Texas Children's Hospital REDCap platform may be used for data collection purposes.

Section G: Sample Size/Data Analysis

G1. Sample Size

How many subjects (or specimens, or charts) will be used in this study?

Local: 20 Worldwide: 20

Please indicate why you chose the sample size proposed:

There are no published and validated data regarding the distribution of pain scores in individuals with EDS. From our clinical experience and the fact that the inclusion criteria require patients have chronic pain, it would be reasonable to estimate the mean pain levels without any oxytocin treatment to be 7 on the BPI scale. With a sample size of 17 individuals who will undergo treatment with placebo and oxytocin (i.e., matched pairs), we will be able to detect a mean difference in BPI scores of 2 or greater with oxytocin as compared to the placebo with a two sided test with alpha error of 0.05 and power of 0.8. This analysis is based on an estimated effect size index dz of 0.73, an SD in the oxytocin group of 0.66 x mean, the SD in the placebo group being 1.25 x mean, and the correlation between the measures being 0.15. Additionally, we will enroll 3 more participants to account for a drop out rate of 15%. Thus the total sample size would be 20

G2. Data Analysis

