Provide a description of your plan for data analysis. State the types of comparisons you plan (e.g. comparison of means, comparison of proportions, regressions, analysis of variance). Which is the PRIMARY comparison/analysis? How will the analyses proposed relate to the primary purposes of your study?

The primary goal of this study is to compare the change in pain scores between the pre and post placebo treatment period vs pre and post IV oxytocin treatment period.

Changes from baseline to endpoint will be evaluated by paired T test

Baseline and endpoint that will be compared:

- 1) Maximum pain level, minimum pain level, average pain, and pain-effect scores (using the BPI) in the days prior to each infusion period (placebo and oxytocin) and maximum pain level, minimum pain level, average pain and pain-effect scores (using the BPI) in the days prior to each infusion period (placebo and oxytocin) and average pain and pain-effect scores in the days after each infusion period.
- 2) Comparing the difference in maximum pain level, minimum pain level, average pain and pain-effect scores (using the BPI) pre and post infusion between placebo and oxytocin treatment.
- 3) Simple pain scale scores (NPRS) prior to infusion and simple pain scale scores 2 hours after the infusion on every day of infusion in both infusion periods (placebo and oxytocin).
- 4) Anxiety and depression scores prior and post infusion periods and comparing scores following placebo and oxytocin treatments
- 5) Changes in heart rate, inter-beat-interval (IBI), and physical activity as measured by ACTIHEART comparing data collected prior, during and after placebo and oxytocin treatments.

In addition we will compare heart rate, blood pressure with oxytocin infusion compared to levels with placebo. We will compare oxytocin levels in the plasma prior to the first infusion, immediately after the first infusion and 2 hours after the first infusion for both placebo and oxytocin.

P-values of 0.05 or less will be considered statistically significant

Section H: Potential Risks/Discomforts

H1. Potential Risks/Discomforts

Describe and assess any potential risks/discomforts; (physical, psychological, social, legal, or other) and assess the likelihood and seriousness of such risks:

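### The sample size calculation gives 5% alpha and 80% power for one test of an unnamed BPI score, while the analysis plan tests four BPI scores, each at 0.05, with none primary

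*Combined protocol and SAP*

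**What the plan says.** **G1, Sample Size.** The calculation is for matched pairs, two-sided alpha 0.05 and power 0.8: "we will be able to detect a mean difference in BPI scores of 2 or greater with oxytocin as compared to the placebo". The inputs begin "This analysis is based on an estimated effect size index dz of 0.73, an SD in the oxytocin group of 0.66 x mean"; the placebo SD is 1.25 times a mean and the correlation is 0.15. G1 expects a mean pain level of 7 on the BPI without oxytocin. It asks for 17 evaluable women and 20 enrolled.

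**G2, Data Analysis.** The form asks: "Which is the PRIMARY comparison/analysis". The answer begins: "The primary goal of this study is to compare the change in pain scores between the pre and post placebo treatment period", and sets that change against the change over the oxytocin period. Changes are tested by paired t test. Item 2 of the list applies this contrast to four scores: "Comparing the difference in maximum pain level, minimum pain level, average pain and pain-effect scores (using the BPI) pre and post infusion". The decision rule for everything is "P-values of 0.05 or less will be considered statistically significant". G2 gives no primary score, testing order, composite or adjustment.

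**Section D, Purpose and Objectives.** There is one primary outcome, change in reported pain, "as assessed by the following questionnaires: Numerical pain rating scale, Brief Pain Inventory, and McGill Pain Questionnaire".

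**F2, Procedure.** Pain questionnaires are completed in a six-day pre-infusion period. The BPI is also given on infusion days, and again on days 1, 3 and 5 after infusion. G2 refers only to the days before and after each infusion period and does not say how they are combined.

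**The concern.** An alpha and a power describe a particular test. The plan identifies the instrument used for sizing, the contrast and the method, but not the score or the summary of days. Four BPI scores fit the description, and the primary outcome adds two more instruments.

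The missing choice decides what counts as a positive result. If any one score below 0.05 is enough, the chance of a false-positive finding is above 5%. If all must be significant, or if the threshold is split, power falls below 80%. If the scores disagree, the plan gives no agreed reading of the trial.

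**Working it through.** **Inputs from G1 and G2:** two-sided alpha 0.05; power 0.80; 17 pairs; dz = 0.73; difference 2; SDs 0.66 × mean (oxytocin) and 1.25 × mean (placebo); correlation 0.15; dropout 15%; four BPI scores. **Assumptions:** equal correlation between the scores (the documents give none, so a range is shown), and dz = 0.73 for every score where joint or Bonferroni power is given.

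**1. The plan's own figure.** Paired t power comes from the noncentral t distribution with n − 1 degrees of freedom and noncentrality dz × √n. For n = 17 this is 0.73 × √17 = 3.01, and power is 80.7%. For n = 16 power is 77.9%, so 17 is the smallest n that reaches 80%. Enrolment: 17 / 0.85 = 20. G1 reproduces.

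**2. False-positive risk if any one score counts.** With independent scores it is 1 − 0.95⁴ = 18.5% for four, and 1 − 0.95³ = 14.3% for the three intensity scores (maximum, minimum, average). With correlated scores it was simulated (17 pairs, 200,000 trials per value):

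| Correlation between scores | Four scores | Three intensity scores |
|---|---|---|
| 0.5 | 15.9% | 12.7% |
| 0.7 | 13.4% | 11.1% |
| 0.9 | 9.6% | 8.5% |

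**3. Power under other rules (four scores, 17 pairs).**
- Any one counts: about 97% at correlation 0.5 and 89% at 0.9, obtained with the error rates in step 2.
- All four must be significant: about 56% at 0.5, 62% at 0.7 and 70% at 0.9.
- Bonferroni, 0.05 / 4 = 0.0125 per score: 58.6% for a given score with 17 pairs and 69.0% if all 20 complete. Reaching 80% takes 25 pairs, and 25 / 0.85 = 29.4, so 30 enrolled.

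**4. Do the SD inputs identify the score?** SD of the difference = √(SDp² + SDo² − 2 × 0.15 × SDp × SDo), and dz = 2 / that SD.
- Levels of 7 (printed) and 5 (7 less the printed difference of 2): SDp = 8.75, SDo = 3.30; √(76.56 + 10.89 − 8.66) = 8.88; dz = 0.23; power 14% with 17 pairs.
- Both multipliers applied to 2: SDs 2.50 and 1.32; SD of difference 2.65; dz = 0.756; n = 16.
- Changes of 1.5 (placebo) and 3.5 (oxytocin), neither printed: SDs 1.875 and 2.31; SD of difference 2.75; dz = 0.728; n = 17.

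The printed dz implies an SD of the within-person difference of 2 / 0.73 = 2.74. None of these readings points to a particular BPI score.

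**The case against.** **It is a pilot.** True, and this bears on how much weight the point carries. But G1 and G2 themselves set a formal alpha, power and significance threshold, and asking which test they belong to is not asking for a larger trial.

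**G1 hints at the score.** Its mean of 7 is described as a level of pain, which suggests an intensity score and not pain-effect. That stands, but maximum, minimum and average remain open, and the any-one risk for those three is still about 8.5% to 13% at correlations of 0.9 to 0.5.

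**Item 1 of G2 might narrow the choice.** Its post-infusion part lists only "average pain and pain-effect scores in the days after each infusion period". The item repeats itself and looks like an editing slip, and item 2 restores all four scores, so nothing should be built on it.

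**Stronger readings a reader might infer, which the documents do not support:**
- *No test is identified at all.* The instrument for sizing, the contrast and the paired t test are all stated. The score, the summary of days and a multiplicity rule are missing.
- *The true false-positive rate is 18.5%.* This needs uncorrelated scores from one questionnaire in the same women, and a rule that any score counts. The plan states no such rule.
- *The sample size is wrong, or the real power is 14%.* The 14% follows only if the multipliers apply to levels of 7 and 5. G1 does not say so, and 17 follows correctly from dz = 0.73. Equally, the change-score reading that recovers 0.73 uses means that are not printed, so the SD inputs cannot be dismissed as a trivial gap.
- *Only one named score will do, or nothing can be repaired later.* A prespecified composite is also a single test. Adjusting over the four listed scores would still control error for that family later, at the lower power in step 3.

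**Conclusion.** The concern holds in this form: the 5% and 80% in G1 describe one paired test whose BPI score and day summary are not named, and the rule in G2 does not deliver 5% across the scores it lists. If any one score counts, the risk is about 10% to 16% for four scores at correlations of 0.9 to 0.5. The Bonferroni alternative leaves 59% power for a score with 17 pairs. These figures rest on assumed correlations, and the power figures also on dz = 0.73 for each score. They do not include the numerical pain scale or the McGill.

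The 80% with 17 pairs (20 enrolled) stands for one test if the SD of the within-person difference is about 2.74. The printed SD inputs do not establish that value. This should be fixed; it does not invalidate the design.

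**What to change.** Before outcome data are examined, make matching edits in Section D, G1 and G2:

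1. Name one primary BPI endpoint, either one score or one prespecified composite. The choice is the investigators'.
2. State which pre-infusion and post-infusion days enter and how they are summarised, for example the mean of the pre-infusion days against the mean of post-infusion days 1, 3 and 5. Naming a score alone would still leave several possible primary tests.
3. Test it once, by two-sided paired t test at 0.05, on the difference in change between the placebo and oxytocin periods.
4. Make the other BPI scores, the numerical pain scale and the McGill secondary, reported with 95% confidence intervals.
5. In G1, say whether the SDs are of levels or of changes, print the means they multiply, and state that 80% power with 17 pairs assumes an SD of the within-person difference of about 2.74. If the named endpoint does not support that value, the power statement must be redone.

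The cost is text only: no added visits or data, and no added participants while the assumed SD stands. The downside is that a significant result on a score not chosen could no longer be claimed as the primary finding, and the chosen score may prove the less responsive one.
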